Additionally, recent review of Moffitt Cancer Center internal data suggests that patients with greater than 5 positive lymph nodes are at a higher risk of regional failure, with locoregional control at 3 years of 94.9% for 1-5 lymph nodes vs 80.1% for > 5 lymph nodes (p = 0.001). By restricting patients to T1-2 N0-1 with 5 or less lymph nodes and a smoking history of 10 pack years or less, 3-year locoregional control of patients treated with radiation alone at Moffitt Cancer Center was 94.7% (n=81) compared to 95.9% with concurrent radiotherapy and systemic therapy (n=98) (personal communication [name]).

In a retrospective analysis of 44 patients, decrease in nodal size of  $\geq$  40% was associated with a locoregional control (LRC) of 100% at 2 years, compared with 78% for a decrease of < 40%. Retrospective review of a Moffitt cohort (n=49) suggests that a cut point of 32% reduction resulted in 100% LRC and DFS (Figure 2A&B). Of note, half of these patients were treated with radiation alone.

In the mathematical modeling of radiation treatment response, there is a suggestion of a more robust treatment response by hyperfractionation when the PSI is > 0.75 (Figure 3).

[figure not shown]

Figure 3: Model of tumor response at 4 weeks by initial pretreatment PSI.

We therefore hypothesize that by personalizing the fractionation, we will increase the number of patients achieving a 32% reduction by week 4.

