#### **3.2 SECONDARY OBJECTIVES**

- Rate of complete response by CT at 2 months or PET/CT at 3 months following completion of therapy.
- Correlate response and outcome to pre-treatment and during treatment radiomics features on PET/CT/MRI.
- Correlate response and outcome to mathematical models of tumor growth and death dynamics pre-treatment and during treatment.
- Correlate RSI/GARD with mid-treatment and post-treatment response.
- Correlate clearance of HPV in serum/oral gargle specimens with mid-treatment and posttreatment response.

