# 7.3 STUDY SCHEDULE

		On Treatment					
Assessments	Pre-Study (within 90 d. of Tx start)	First day, prior to RT (within5 days prior)	Once-a- WeekDuring RT	Week 4 During RT	End of Tx (+/- 3 days)		
Evaluations							
Rad Onc EvalH&P, ECOG, Weight	х		Х				
Imaging							
CT# or MRI of primary and neck a,b	Xh	Х		х			
PET/CT	Xc						
Labs							
Urine PregnancyTest (only Females of Child bearing potential)	х						
Tumor Tissue for RSI	Х						
Oral Gargle for HPV e	Х		х	х	х		
Plasma for HPV f	Х		Х	Х	Х		

	From End of Treatment							
Assessments	4 Wks +/- 14 days	2-3 mo +/- 14 days d	6 mo +/- 14 days	12 mo +/- 14 days	18 mo +/- 14 days	24 mo +/- 14 days	Time of disease progression if sooner than 24 mos g	End of study if the patient is off the study before 24 mos with any reasons g
Evaluations								
Rad Onc Eval H&P, ECOG, Weight	х	х	х	Х				

Assessments	4 Wks +/- 14 days	2-3 mo +/- 14 days d	6 mo +/- 14 days	12 mo +/- 14 days	18 mo +/- 14 days	24 mo +/- 14 days	Time of disease progression if sooner than 24 mos g	End of study if the patient is off the study before 24 mos with any reasons g
Imaging								
CT# or MRI of primary and neck a,b		Xc						
PET/CT		Xc						
Labs								
Urine PregnancyTest (only Females of Child bearing potential)								
Tumor Tissue for RSI								
Oral Gargle for HPV e		х	х	х	х	Х	х	Х
Plasma for HPV f		Х	Х	Х	Х	Х	Х	Х

aInterim MRI or CT for response assessment.

bCT at day 1 and week 4 may be done using Department of Radiation Oncology CT SimulationcAt physician discretion. Pre-treatment PET/CT can be up to 180 days prior to CT simulation. dA CT at 2 months and/or PET/CT at 3 months may be done at physician discretion.

eOral Gargle for HPV to be collected at pre-therapy, during treatment at week 1, week 2, week 3, week 4, end of treatment, 3 months post-RT, 6 months post-RT, 12 months post-RT, 18 months post-RT, 24 months post-RT, time of diseaseprogression (if sooner than 24 months), and end of study (if patient discontinues the study with any reason sooner than 24 months). See 7.2.4/7.2.5 for collection windows.

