# **10 STATISTICAL CONSIDERATIONS**

# **10.1 STATISTICAL AND ANALYTICAL PLANS**

Demographic information such as age and race will be tabulated. Descriptive statistics, including means, standard deviations, and ranges for continuous parameters, as well as percents and frequencies for categorical parameters, will be presented.

The effectiveness of PSI to select fractionation schema will be assessed by percent response at the 4th week of treatment. One-sided 95% confidence interval for the percent response at the 4th week of treatment will be also reported. A proportion difference test will be performed to test a difference of complete response rate from a target of 49%.

As for secondary endpoints, response will be correlation with pre-treatment and during treatment radiomics features on PET/CT/MRI using two sample t-tests and univariate/multivariate logistic regression analysis as appropriate. Correlation of response and outcomes to the mathematical models of tumor growth and death dynamics pre-treatment and during treatment will be performed using logistic regression analysis.

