# **10.2 DESCRIPTION OF STATISTICAL METHODS**

# 10.2.1 GENERAL APPROACH

This protocol is a single arm, phase II design with a primary endpoint of 63% of patients achieving  $a \ge 32\%$  reduction in tumor volume by week 4. This study will test the null hypothesis that the true response rate is equal to or less than a historical control of  $49\%^{11}$  versus the alternative hypothesis that it is greater than 49%.

Based on Fleming's 2-stage group sequential design, a total of 60 subjects will provide approximately 79% power with a type I error rate of 0.1 to detect a true response rate of 63%. The study will enroll subjects in two stages, with 49 subjects in the first stage. One interim efficacy/futility analysis will be conducted when the first 49 subjects have completed the study treatment and response evaluation. If the number of responsive patients is equal to or less than 27, the trial will be stopped for futility. If the number of responsive patients is equal to or greater than 30, the trial will be stopped for efficacy. Otherwise, the trial will continue to the second stage by enrolling 11 additional subjects.

At the final analysis with the total 60 subjects at the second stage, if there are equal to or more than 35 responsive patients, it will be concluded that the null hypothesis is rejected and the study treatment will be promising.

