# 10.2.3 ANALYSIS OF THE SECONDARY ENDPOINT(S)

- Assess complete response by CT at 2 months or PET/CT at 3 months following completion of therapy. This will be compared against historical controls.
- Response correlation with pre-treatment and during treatment radiomics features on PET/CT/MRI:

Radiomics features based on CT, MRI, PET-CT, noted during various imaging scans (pre-treatment, at 4 week of RT, and follow-up scan) will be correlated with the overall oncological response and outcome

Response correlation at 4 weeks and post treatment imaging with clearance of HPV from serum or oral gargle, and RSI/GARD.

 Correlate response and outcome to mathematical models of tumor growth and death dynamics pre-treatment and during treatment: Mathematical models will be generated based on the pattern of tumor growth and response as depicted by tumor volume measurement on various scans. These mathematical models will be validated by correlating with the overall response and oncological outcome

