# 10.3 SAMPLE SIZE

60 patients total. Total accrual time is expected to be 30 months.

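### Oncological outcome is analysed by logistic regression with no definition, horizon or censoring rule, although early exit is foreseen and no disease evaluation is scheduled after month 12

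*Combined protocol and SAP*

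**What the plan says.** - Section 3.2 lists a secondary objective with two targets: "Correlate response and outcome to mathematical models of tumor growth and death dynamics pre-treatment and during treatment". Section 10.1 takes up both targets under "Correlation of response and outcomes to the mathematical models of tumor growth and death dynamics" and assigns them one method, stating that this work "pre-treatment and during treatment will be performed using logistic regression analysis".
- Section 10.2.3 says that radiomics features "will be correlated with the overall oncological response and outcome", and that the mathematical models will be validated against response and oncological outcome. It names no method, time point or event for outcome.
- Section 4.2 defines two endpoints: volumetric response at week 4, and complete response at 2–3 months. Oncological outcome is not defined there or elsewhere.
- In the section 7.3 schedule, the row "Rad Onc EvalH&P, ECOG, Weight" is marked after treatment at 4 weeks, 2–3, 6 and 12 months, and is blank at 18 and 24 months. Post-treatment imaging is marked only at 2–3 months. Oral gargle and plasma continue to 24 months. Two further columns cover progression before 24 months and leaving the study early; only gargle and plasma are marked there, and a footnote takes the patient off trial afterwards.
- Section 2.3 gives background figures for locoregional control and disease-free survival, including "3-year locoregional control of patients treated with radiation alone at Moffitt Cancer Center was 94.7% (n=81" in a population restricted much like this one.
- Section 10.3: "60 patients total. Total accrual time is expected to be 30 months". Section 10.2.1: "The study will enroll subjects in two stages, with 49 subjects in the first stage".

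**The concern.** Logistic regression needs a yes/no status that means the same thing for every patient. Week-4 response and complete response have that. An oncological outcome such as locoregional control does not, unless the plan fixes a horizon and says what happens to patients not observed to it. As written, anyone without a recorded event is a non-event, however short the observation.

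Sections 3.2 and 10.2.3 separate response from outcome, so the word cannot simply be read as the two response endpoints. After month 12 the schedule contains nothing that would establish disease status, although it expects progression to be known up to 24 months.

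At stake is one part of the secondary analyses. An association built on two or three failures, with uneven observation, could be presented as validation of the model that assigns fractionation.

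**Working it through.** **Inputs.** N = 60, or 49 if the trial stops at stage 1 (10.2.1). Three-year locoregional failure 1 − 0.947 = 0.053 (2.3). Pessimistic alternative 0.10, because section 2.3 also cites a radiotherapy-alone trial with control above 90%; no time point is given there, so treating it as a 3-year rate is my assumption. Accrual 30 months (10.3), taken as even. About 1.5 months of radiotherapy (assumption). Constant hazard (assumption).

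**The plan's own figure.** It states none for the outcome correlations. Its only power figure, about 79% at type I error 0.1, concerns week-4 response. The exact calculation, P(X1 ≥ 30) + Σ over x = 28, 29 of P(X1 = x)·P(X2 ≥ 35 − x), gives 0.791 at 63% and 0.093 at 49%. That figure reproduces and has no bearing on outcome.

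**Weight given to an early exit.** λ = −ln(0.947)/36 = 0.00151 per month.
- Failure probability by 3 months: 1 − exp(−3λ) = 0.45%.
- By 24 months: 1 − exp(−24λ) = 3.6%.

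An event-free exit at 3 months carries about one eighth of the information on failure, yet enters the logistic model as a full non-event.

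**Staggered entry.** With data cut at C months after first enrolment, the number who could have m months after radiotherapy is 60 × (C − 1.5 − m)/30, ignoring withdrawals:

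| Cut-off C | 12 months' follow-up | 24 months' follow-up |
|---|---|---|
| 33 | 60 × 19.5/30 = 39 | 60 × 7.5/30 = 15 |
| 42 | 60 × 28.5/30 = 57 | 60 × 16.5/30 = 33 |
| 55.5 | 60 | 60 × 30/30 = 60 |

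The plan states no cut-off, so this component ranges from large to nil. Early exit remains in every case.

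**Expected locoregional failures in 60 patients**, 60 × (1 − exp(−λt)):

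| 3-year control | by 12 months | by 24 months | by 36 months |
|---|---|---|---|
| 94.7% | 1.1 | 2.1 | 60 × 0.053 = 3.2 |
| 90% | 2.1 | 4.1 | 60 × 0.10 = 6.0 |

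The 95% binomial range at 36 months is 0–7 at 94.7% and 2–11 at 90%. At 94.7%, P(5 or fewer) = 0.90 and P(1 or none) = 0.17. With 49 patients: 49 × 0.053 = 2.6.

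**What so few events can show.**
- If all 3 failures fell in one half of a 30/30 split, the exact one-sided p is C(30,3)/C(60,3) = 4,060/34,220 = 0.12, or 0.24 two-sided. No median-split predictor could reach 0.05.
- For a Cox model with a 50/50 split, power is Φ(√(d/4)·ln HR − 1.96). With d = 3 this is 9% at HR 2, 16% at HR 3 and 29% at HR 5.
- The hazard ratio detectable with 80% power is exp(2.80/√(3.18/4)), about 23.
- Ten failures would need 10/0.053, about 189 patients (100 at a 10% failure rate).

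**The case against.** The best defence is that both endpoints in section 4.2 are binary at a fixed time, so logistic regression is the right tool for them; that locoregional control and disease-free survival appear only as background; and that with about three events a Cox model is hardly better than a logistic one. The first part stands, and so does the last: censoring corrects how observation time is counted but creates no information. What does not stand is reading outcome as response, because the objectives and section 10.2.3 name them separately.

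Several stronger readings are tempting and are not supported:

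- **That a multivariable outcome model is planned.** Section 10.1 assigns univariate and multivariate logistic regression to response against radiomics features. For outcomes it says only logistic regression.
- **That only 33 of 60 patients will have 12 months and 9 of 60 will have 24 months of follow-up.** This follows from a data cut at 30 months: (30 − 13.5)/30 = 55% and (30 − 25.5)/30 = 15%. But 30 months is the accrual time in section 10.3. With that cut, 60 × 4.5/30 = 9 patients would lack a 3-month assessment and the last enrolled would lack the week-4 scan, which does not fit a final analysis of 60 or a 24-month schedule. The Study Summary's ~30-month study duration and ~33-month participant duration need reconciling, but they do not establish a 30-month cut.
- **That progression after month 12 will go unrecorded.** The schedule has a column for progression before 24 months. What is missing is a scheduled evaluation that would establish it; routine follow-up may still do so.
- **That the plan defines outcome as locoregional control or disease-free survival.** It does not. This is the natural reading of the background, and disease-free survival would add events that the documents do not quantify for this population.

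**Conclusion.** The point holds in a limited form. Section 10.1 applies logistic regression to an outcome that is undefined and has no horizon or censoring rule. The schedule itself foresees exit before 24 months, and it marks no disease evaluation after the month-12 history and examination. If outcome means locoregional control or disease-free survival, patients who leave early event-free are counted as full non-events. The added effect of staggered entry cannot be sized, because no data cut-off is stated.

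About 3.2 locoregional failures are expected in 60 patients by 3 years, and about 2 by 24 months (4 if 3-year control were 90%). These counts assume that the institution's 94.7% applies here and, for 24 months, a constant hazard. At that size an outcome association can only be described, whichever model is used.

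A reader might infer that the trial's main conclusion is at risk. It is not: the week-4 test, the stopping rules and the complete-response analysis do not use this outcome.

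**What to change.** 1. Keep logistic regression for week-4 response and complete response.
2. Define the oncological outcome, for example locoregional control and disease-free survival, as time from start of radiotherapy to the event, censored at the last disease assessment. State the data cut-off and how death without locoregional failure is handled.
3. Report Kaplan-Meier estimates and, at most, single-covariate Cox models with Firth penalisation, with intervals and labelled descriptive.
4. At the existing 18- and 24-month sampling visits, record disease status as known from routine follow-up, with the date of the last assessment. Censoring at that date, and not at the sample date, keeps the analysis honest where no recent assessment exists.

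The cost is some SAP wording and one data field at two visits already in the schedule. The real concession is that the outcome correlations can no longer be presented as validation of the mathematical model. With two or three failures they could not have borne that weight in any case.

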# **10.2 DESCRIPTION OF STATISTICAL METHODS**

# 10.2.1 GENERAL APPROACH

This protocol is a single arm, phase II design with a primary endpoint of 63% of patients achieving  $a \ge 32\%$  reduction in tumor volume by week 4. This study will test the null hypothesis that the true response rate is equal to or less than a historical control of  $49\%^{11}$  versus the alternative hypothesis that it is greater than 49%.

Based on Fleming's 2-stage group sequential design, a total of 60 subjects will provide approximately 79% power with a type I error rate of 0.1 to detect a true response rate of 63%. The study will enroll subjects in two stages, with 49 subjects in the first stage. One interim efficacy/futility analysis will be conducted when the first 49 subjects have completed the study treatment and response evaluation. If the number of responsive patients is equal to or less than 27, the trial will be stopped for futility. If the number of responsive patients is equal to or greater than 30, the trial will be stopped for efficacy. Otherwise, the trial will continue to the second stage by enrolling 11 additional subjects.

At the final analysis with the total 60 subjects at the second stage, if there are equal to or more than 35 responsive patients, it will be concluded that the null hypothesis is rejected and the study treatment will be promising.

# 10.2.2 ANALYSIS OF THE PRIMARY EFFICACY ENDPOINT(S)

The effectiveness of PSI to select fractionation schema will be assessed by percent response at the 4th week of treatment. One-sided 95% confidence interval for the percent response at the 4th week of treatment will be also reported. A proportion difference test will be performed to test a difference of complete response rate from a target of 49%.

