#### **3 OBJECTIVES AND PURPOSE**

#### 3.1 PRIMARY OBJECTIVE

For patients with HPV+ squamous cancer of the oropharynx, fractionation of radiation will be individualized based on their PSI. Response will be measured after 20 days of RT as assessed by CT or MRI, as described in section 10.0. Primary objective is to increase the rate of response of  $\geq$  32% at 20 days to 63% of patients, above the expected 49%.

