4.2.2 Post Treatment response at 2-3 months after RT

A complete response will be defined as resolution of all disease in the head and neck by CT at 2 months or PET/CT at 3 months. On CT scan, nodes less than 1 cm in short axis without evidence of necrosis will be defined as negative. On PET/CT, resolution of hypermetabolism to maximum SUV of 3 or less will be defined as negative, even with evidence of a node larger than 1 cm in short axis on CT scan. CT scans or PET scans which do not meet these criteria will be reviewed at the Moffitt H&N tumor board for determination of response.

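### The primary-analysis section tests complete response, a secondary endpoint, against the 49% benchmark for week-4 volume reduction, and does not say whether the test is one-sided

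*Combined protocol and SAP*

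**What the plan says.** **Section 10.2.2 (analysis of the primary efficacy endpoint).** Two sentences refer to week-4 response: one makes it the measure of effectiveness, and the next reads "One-sided 95% confidence interval for the percent response at the 4th week of treatment will be also reported". The test follows: "A proportion difference test will be performed to test a difference of complete response rate from a target of 49" per cent. Section 10.1 carries the same test sentence. Neither place gives a side or a significance level for the test.

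**Section 10.2.1 (general approach).** The primary endpoint is a tumor volume reduction of at least 32% by week 4. "This study will test the null hypothesis that the true response rate is equal to or less than a historical control of" 49%. The alternative has one side only: "versus the alternative hypothesis that it is greater than 49" per cent. Type I error is 0.1, with about 79% power at a true rate of 63%. Of the first 49 patients, 27 or fewer responders stop the trial for futility and 30 or more stop it for efficacy. Otherwise 11 more patients enter, and 35 or more responders among 60 reject the null hypothesis.

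**Section 3.1 (primary objective).** "Primary objective is to increase the rate of response of" at least 32% to 63% of patients, against an expected 49%. The endpoint paragraph of the Study Summary uses the same two rates.

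**Complete response.** Section 3.2 lists as a secondary objective: "Rate of complete response by CT at 2 months or PET/CT at 3 months following completion of therapy". Section 4.2.2 defines the term: "A complete response will be defined as resolution of all disease in the head and neck". The assessment there is a CT two months after radiotherapy or a PET/CT at three months. Section 10.2.3 gives its comparison: "This will be compared against historical controls".

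**The concern.** The test sentence joins two things that do not belong together. Its endpoint, complete response, has its own definition, its own assessment time and its own comparison in Section 10.2.3. Its null value, 49%, belongs to the on-treatment volume response. Nowhere do the documents give 49% as a complete response rate.

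The sentence also speaks only of a difference, while Section 10.2.1 has a one-sided alternative. An analyst who follows Section 10.2.2 literally would test a post-treatment endpoint against an unrelated benchmark and call that the primary analysis. An analyst who sees the slip and substitutes the week-4 endpoint must still choose a side. Near the decision boundaries, that choice determines whether the reported p-value agrees with the declared result.

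**Working it through.** **1. Inputs, all from Section 10.2.1.** Null rate 0.49; alternative 0.63; type I error 0.1; stage 1 n = 49 (futility at 27 or fewer, efficacy at 30 or more); stage 2 n = 11; final success at 35 or more of 60.

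**2. Reproducing the plan's own figure.** With X1 ~ Bin(49, p) and X2 ~ Bin(11, p):

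P(reject) = P(X1 ≥ 30) + P(X1 = 28)·P(X2 ≥ 7) + P(X1 = 29)·P(X2 ≥ 6)

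- p = 0.49: 0.0580 + 0.0347 = 0.0928, within the nominal 0.1.
- p = 0.63: 0.6611 + 0.1303 = 0.7915, matching the stated 79%.

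A single-stage normal approximation with n = 60 and alpha 0.1 gives power 0.821 one-sided and 0.706 two-sided. The stated power therefore belongs to a one-sided test.

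**3. The sections side by side.**

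| | 10.2.1 | 10.1 and 10.2.2, test sentence | 10.2.3 |
|---|---|---|---|
| Endpoint | ≥32% volume reduction by week 4 | Complete response | Complete response |
| Comparator | 49% | 49% | Historical controls, no figure |
| Side | One-sided, greater | Not given | Not given |
| Level | 0.1 | Not given | Not given |

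The middle column takes its endpoint from the right and its null value from the left.

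**4. What the missing side does once the endpoint is corrected.** These p-values treat n as fixed and are not adjusted for the two stages. Score test: z = (x/n − 0.49)/√(0.49 × 0.51/n). For 35/60, z = (0.5833 − 0.49)/√(0.2499/60) = 1.446. The exact two-sided p sums the probabilities of all outcomes no more likely than the one observed.

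| Result (a success under 10.2.1) | One-sided p: score, exact | Two-sided p: score, exact |
|---|---|---|
| 30/49 | 0.043, 0.058 | 0.087, 0.115 |
| 35/60 | 0.074, 0.094 | 0.148, 0.157 |
| 36/60 | 0.044, 0.057 | 0.088, 0.094 |

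All the one-sided values are below 0.10. Two-sided, 35/60 exceeds 0.10 by either method, and 30/49 exceeds it by the exact method.

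**5. How often this would happen at a true rate of 63%.** Under the two-stage rule the outcome probabilities are 0.1126 for 30/49, 0.0395 for 35/60 and 0.0408 for 36/60. The share of successes with two-sided p above 0.10 is:

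- score: 0.0395/0.7915 = 5.0%;
- exact, as defined above: (0.0395 + 0.1126)/0.7915 = 19.2%;
- exact, doubling the one-sided p: 36/60 gives 2 × 0.0574 = 0.115 and now also exceeds 0.10, so (0.0395 + 0.1126 + 0.0408)/0.7915 = 24.4%.

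**6. Secondary: the interval level.** One-sided 95% lower bounds, n treated as fixed:

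| Result | Clopper-Pearson | Wilson | Wald |
|---|---|---|---|
| 30/49 | 48.5% | 49.5% | 49.8% |
| 35/60 | 46.9% | 47.7% | 47.9% |
| 36/60 | 48.6% | 49.4% | 49.6% |

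At 35/60 the bound lies below 49% with every method, although Section 10.2.1 rejects the null. At a true rate of 63%, such conflicts make up 5.0% of successes (Wilson or Wald) to 0.1929/0.7915 = 24.4% (Clopper-Pearson). The lowest one-sided 90% bound for any success is 49.2% (Clopper-Pearson, 35/60), so a 90% bound never conflicts. An exact calculation that respects the two stages (stagewise ordering) gives the same picture for 35/60: p = 0.0928, 95% bound 46.9%, 90% bound 49.3%.

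**The case against.** The strongest reply is that the plan already answers the question. Section 10.2.1 fixes the endpoint, null, alternative, type I error and exact counts, and Section 10.2.4 repeats the interim rule. The two sentences before the faulty one refer to week-4 response, and complete response is handled separately in Section 10.2.3. The word complete is most likely a stray. This stands: it makes the trial decision safe and limits the weight of the point. It does not make the sentence correct. The sentence appears twice, it is the only test named in the section devoted to the primary analysis, and it uses a term that the protocol defines as something else.

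A second reply is that testing a difference is loose wording and not a claim of two-sidedness, since the neighboring interval and Section 10.2.1 are both one-sided. That is the more natural reading. The two-sided figures therefore show what the ambiguity could cost and do not predict what will be done. Even then, success is decided by counts, so a large two-sided p would be an awkward report and not a reversal.

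Third, a 95% bound beside a test at 0.1 is a common supplementary choice, and nothing makes it a decision criterion. Agreed; that part is optional.

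**Conclusion.** The concern holds. As written, Sections 10.1 and 10.2.2 test a secondary endpoint against the primary endpoint's benchmark and leave the side open, in contradiction to Section 10.2.1. It should be corrected, but it is an error of text and not of design. The boundaries, sample size and stated power are sound and unaffected.

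The practical effect is confined to reporting. Under a two-sided reading, a result at the final boundary (35/60) would be declared a success with a p-value near 0.15. The 5% to 24% range for such conflicts assumes a true response rate of 63%, a 0.10 threshold and fixed-sample p-values, and it varies with the test chosen. The consequence of testing complete response itself cannot be sized, because the documents give no expected rate for it.

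**What to change.** In Sections 10.1 and 10.2.2, replace the test sentence with wording such as:

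> The primary test is of H0: p ≤ 0.49 against p > 0.49, where p is the proportion of patients with at least 32% tumor volume reduction at week 4. It has a one-sided type I error of 0.10 and is decided by the boundaries in Section 10.2.1 (at least 30 of 49 at stage 1, or at least 35 of 60 at the final analysis).

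Keep complete response in Section 10.2.3 only, against its own historical benchmark, stated and justified there.

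Optionally, add one line on the interval. Either report a one-sided 90% lower bound, naming the method and whether it adjusts for the two-stage design, or state that the 95% bound is descriptive and does not override the Section 10.2.1 decision.

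The cost is one sentence in two places and, if wanted, one further line. Sample size, boundaries and data collection do not change.
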